6.1.2 DOSING AND ADMINISTRATION

Dosage

Azithromycin will be administered at a dose of 7.5mg/kg to a maximum of 500mg/day for 5 consecutive days per week for the first 4 weeks and then 3 consecutive days/week for 4 weeks.

Metronidazole will be administered 10mg/kg twice daily (20mg/kg/day) to a maximum of 1000mg/day for 8 weeks.

Patients who suspect they are intolerant to the medications are advised to contact the study coordinator regarding any new symptoms (predefined as new onset of emesis, significant nausea, abdominal pain or diarrhoea).

At the discretion of the responsible physician, patients can be instructed to reduce the dose of metronidazole by 25% to 15mg/kg/day and divide the frequency to 3 times daily. Any dosage change will be appropriately documented in the CRF.

Formulations

Azithromycin and metronidazole are both available in 250mg tablets. Azithromycin is also commercially available as an oral suspension. Metronidazole is not commercially available as an oral suspension, but a suspension can be prepared by a pharmacy from 250mg tablets.

6.2 PREPARATION/HANDLING/STORAGE/ACCOUNTABILITY

6.2.1 ACQUISITION AND ACCOUNTABILITY

The investigational drugs will be acquired at each site independently, and labeled according to FDA labeling requirements found in 21CFR 312.6. The investigational Pharmacy at each site will dispense study drugs following enrollment and randomization according to study protocol. For Azithromycin 250 mg in tablets and suspension are available. Metronidazole is available in 250 mg tablets and pharmacies can also prepare an extemporaneous compound of the Metronidazole liquid (to be refrigerated).

Each of the participating study sites will dispense and label study drugs according to local guidelines. For example, at UNC, Vestigo software is used for the management of inventory and accountability as well as labeling the product with an outpatient label. Return of unused study drug and accountability on those returns will be performed using this same software system.

Subjects will be seen in dedicated outpatient clinics during this study and the local study coordinator will be delivering the appropriately dosed and labelled study drugs to the child/parent and explaining the medication and use and storage to them.

6.2.2 FORMULATION, APPEARANCE, PACKAGING, AND LABELING

Azithromycin and metronidazole are both available in 250mg tablets. Azithromycin is also commercially available as an oral suspension as 100 mg/5 mL. Metronidazole is not commercially available as an oral suspension, but a suspension can be prepared by a pharmacy from 250mg tablets.

Both drugs are FDA-approved and commercially available, most recent product labels are available at the following URLs:

https://www.accessdata.fda.gov/drugsatfda_docs/label/2017/050670s032,050710s046,050711s043,050784s030lbl.pdf

https://www.accessdata.fda.gov/drugsatfda_docs/label/2015/012623s066lbl.pdf

The supplier of the drug may differ from the label provided, but the route, administration, and product information will be the same.

6.2.3 PRODUCT STORAGE AND STABILITY

Azithromycin tablets should be stored between 15° to 30° C (59° to 86° F). Metronidazole tablets should be stored below 77°F (25°C) and protected from light.

Azithromycin for oral suspension is supplied to provide 100 mg/5 mL or 200 mg/5 mL suspension. Dry powder should be stored below 30°C (86°F). Constituted suspension should be stored between 5° to 30°C (41° to 86°F) and discarded when full dosing is completed.

Metronidazole is not commercially available as an oral suspension, but a suspension can be prepared by a pharmacy from 250mg tablets (to be refrigerated).

Both drugs are FDA-approved and commercially available, most recent product labels are available at the following URLs:

https://www.accessdata.fda.gov/drugsatfda_docs/label/2017/050670s032,050710s046,050711s043,050784s030lbl.pdf

https://www.accessdata.fda.gov/drugsatfda_docs/label/2015/012623s066lbl.pdf

The supplier of the drug may differ from the label provided, but the route, administration, and product information will be the same.

6.2.4 PREPARATION

Azithromycin and metronidazole are both available in 250mg tablets. Azithromycin is also commercially available as an oral suspension as 100 mg/5 mL. Metronidazole is not commercially available as an oral suspension, but a suspension can be prepared by a pharmacy from 250mg tablets. Pharmacies at each of the participating study sites will dispense and label study drugs according to local policies.

Both drugs are FDA-approved and commercially available, most recent product labels are available at the following URLs:

https://www.accessdata.fda.gov/drugsatfda_docs/label/2017/050670s032,050710s046,050711s043,050784s030lbl.pdf

https://www.accessdata.fda.gov/drugsatfda_docs/label/2015/012623s066lbl.pdf

The supplier of the drug may differ from the label provided, but the route, administration, and product information will be the same.

6.3 MEASURES TO MINIMIZE BIAS: RANDOMIZATION AND BLINDING

We will randomly allocate the subjects who are identified as having a relapse-associated microbiome into experimental treatment or control arms. The randomization process and creation of randomization envelopes are performed by the study coordinator at the Amsterdam UMC, location AMC. To ensure 1:1 randomization, blocks of 2 will be generated by using CastorEDC for patients randomized to group A. The same number of patients will be randomly allocated in the cohort groups A1 and A2.

Once the temporary ID has been matched with the participant's Study ID, a randomization pdf is created for the Study ID number, with the treatment group assignment and emailed to the local study-coordinator. The study coordinator will then prepare a sealed randomization envelope with a card stating whether they will take antibiotics or not to take antibiotics. The study coordinator will give this envelope to the participant & family to open this envelope in the presence of the local site-study coordinator. The physician will be informed of the outcome of the randomization. A prescription will then be issued by the treating physician. The local site-study coordinator will verify that each patient understands the instructions.

This study will not be blinded.

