4 STUDY DESIGN

4.1 OVERALL DESIGN

The primary hypothesis tested is that administering adjunctive antibiotic therapy to patients with a relapse-associated gut microbiome profile will help to sustain clinical response to standard induction therapy for mild to moderately active Crohn's disease.

To test this hypothesis, patients with a relapse-associated microbiome profile will be identified via baseline stool sample analysis and will be randomly allocated to the treatment arm that will receive antibiotics (azithromycin + metronidazole) on top of SOC induction therapy, or a control arm that will receive SOC induction therapy alone. Patients not achieving clinical remission (PCDAI greater than 10 at week 4), can receive antibiotics (azithromycin/metronidazole), will not be randomized, and will continue to be followed until 52 weeks. This pilot trial is intended to be a smaller version of a larger trial, and will be used to evaluate feasibility including standard deviation of the outcome measures, adherence, and baseline microbiome profiling.

Standard of care (SOC) induction therapy, as started by the responsible physician, for this study will be defined as Crohn's Disease Exclusion diet nutritional therapy (CDED Phase 1 from 0-6 weeks and Phase 2 from 6-12 weeks), in accordance with the recently published RCT for the CDED.²⁴

This is a 52-week, multicenter, randomized, controlled, open-label add-on design clinical trial pilot trial to test the feasibility of a larger trial evaluating the efficacy of adjuvant antibiotic therapy in pediatric patients with mild to moderate CD. This study will not be blinded.

A total of 20 subjects between the ages of 3 and 17 years inclusive will be enrolled in eight investigational sites located in Canada, the United States, the Netherlands and Israel.

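### Section 6.3 does not protect allocation concealment: the arm may reach the local coordinator before the week-4 PCDAI and group are recorded, and fixed blocks of 2 add to the predictability

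*Combined protocol and SAP*

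**What the plan says.** Section 6.3 fixes one block size for Group A ("To ensure 1:1 randomization, blocks of 2 will be generated by using CastorEDC for patients randomized to group A"), asks for exact balance ("The same number of patients will be randomly allocated in the cohort groups A1 and A2") and adds "This study will not be blinded". On the handling of the list it says "The randomization process and creation of randomization envelopes are performed by the study coordinator at the Amsterdam UMC, location AMC". Amsterdam is also an enrolling site (section 1.1; Netherlands addendum, recruitment).

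The steps in section 6.3 run as follows. When the temporary ID has been matched to the Study ID, a pdf is created "with the treatment group assignment and emailed to the local study-coordinator". After that, "The study coordinator will then prepare a sealed randomization envelope", which the family opens in front of the local coordinator. The physician is then told the result.

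The schedule of activities (section 1.3) puts both the PCDAI and randomization at Visit 3, week 4. Section 4.1 removes one group from randomization at that visit: "Patients not achieving clinical remission (PCDAI greater than 10 at week 4"). These children form Group C, for whom antibiotics are available. Children in remission with the relapse-associated profile form Group A and are randomized to A1 (no added antibiotic) or A2. Section 9.3 analyses Group C separately, and section 9.4.2 compares A1 with A2.

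**The concern.** Concealment has to hold until the decision that makes a child eligible for randomization is fixed. Here that decision is a score with a cut-off at 10, obtained by unblinded staff at the same visit. If the arm is known or can be guessed first, a borderline child expected in A1 could be scored above 10. The child would then enter Group C, with access to antibiotics, and leave the A1 versus A2 comparison. With 20 children spread over A, B and C, one or two such moves would matter.

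The point counts even in a pilot. Efficacy in A1 versus A2 remains a primary objective (section 3 and the addendum). The proportion of patients per arm is a feasibility outcome. The addendum also allows pilot data into the full trial if the protocol is not substantially changed.

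**Working it through.** The plan gives no figure for predictability. Its one computed design figure, 25 per arm for the later trial, does not bear on this point.

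**1. Order of steps.** Section 6.3 names one trigger for releasing the arm: the matching of IDs. Sections 1.3, 4.1 and 9.2 put the PCDAI and the A/B/C placement at week 4 but do not tie release of the arm to them. No section requires the score or the group to be entered first. This gap does not depend on block size, because the emailed pdf names the arm in any case.

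**2. Blocks of 2, observer who sees the whole sequence.** Only A1-A2 and A2-A1 are possible.
- Certain: 1 of every 2 = 50%.
- Best guess correct: (0.5 + 1)/2 = 75%, against 50% by chance.

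This describes the Amsterdam coordinator, or every site if lists are kept per site.

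**3. Blocks of 2, local site, one central list.** Assume equal accrual over S sites. The synopsis counts eight sites and lists five. An allocation is certain if it is second in its block and its partner was at the same site: 0.5 × 1/S.
- S = 5: 0.5 × 0.2 = 10%. S = 8: 0.5 × 0.125 = 6%. A simulation of 40,000 runs gives 0.10 and 0.06.
- Best guess correct: 0.10 + 0.90 × 0.5 = 55%, and 0.0625 + 0.9375 × 0.5 = 53%.

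This supposes that the site can tell that its two children share a block, so under equal accrual it is an upper figure. Uneven accrual raises it: four equal sites, the fewest compatible with the cap of 5 per site in section 5.5, give 0.5 × 0.25 = 12.5%.

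**4. Random blocks of 2 and 4, sizes undisclosed, full-sequence observer.** An allocation is certain only after the first two in a block of 4 are alike (probability 1/3), which fixes the next two.
- Certain: 0.5 × 1/3 × 2 = 0.333 per block; divided by the mean length of 3, this is 11%.
- Best guess correct: about 71% by simulation over 10 allocations. In the long run a block of 2 gives 1.5 correct and a block of 4 gives 1/3 × 2.5 + 2/3 × 3 = 2.83, so (1.5 + 2.83)/(2 + 4) = 72%.

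**5. Cost in balance.** The number in Group A is not stated; 6 to 10 is assumed. A difference of 2 arises only if the list stops halfway through a block of 4 whose first two are alike. Let u(k) be the chance that a block ends after k pairs: u(k) = [u(k−1) + u(k−2)]/2, with u(0) = 1 and u(1) = 0.5. Then u(3) = 0.625, u(4) = 0.6875 and u(5) = 0.656. The mean difference is (1 − u) × 1/3 × 2:
- n = 6: 0.375 × 0.667 = 0.25
- n = 8: 0.3125 × 0.667 = 0.21
- n = 10: 0.344 × 0.667 = 0.23

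The largest possible difference is 2.

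**The case against.** Several points on the other side stand.

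- A reader might infer that every second allocation is certain to each site. The documents do not support this: section 6.3 describes one central process, section 4.1 names stratification by microbiome profile only, and lists per site are neither stated nor excluded. No text says that the Amsterdam coordinator scores the PCDAI.
- A reader might infer that the local coordinator holds the arm before the PCDAI is scored. Sections 4.1 and 9.2 read more naturally as placement first and randomization second, and section 6.3 mentions telling the physician only after the envelope is opened. Foreknowledge is permitted, not stated.
- A reader might infer that the envelope is made locally. One sentence gives its creation to Amsterdam, and a later one names only the study coordinator. The text is ambiguous, but either way the local coordinator has been emailed the arm.
- The PCDAI is not purely a clinical judgement: section 8.1 says that blood results are needed to calculate it. Section 2.3.3 leaves families and physicians free to choose treatment outside the study, so a raised score is not the only route to antibiotics.
- It would be too strong to say that diversion could not be detected. Week-4 scores and laboratory inputs are collected and Group C is followed, so borderline scores can be checked against source data and the sequence.
- Exact balance is a defensible aim in a very small pilot, and the addendum concedes that the numbers cannot settle efficacy.

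None of this supplies the missing rule that the score and group be recorded before the arm is released.

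**Conclusion.** The concern holds as a weakness in the stated procedure. The arm goes to local staff on ID matching, in an unblinded trial, with no requirement that the week-4 PCDAI and group be fixed first. The documents do not show that selection occurred or would occur, and they give no basis for a size of bias in A1 versus A2. Only predictability can be quantified: 50% certain and 75% guessable for a full-sequence observer, and about 6–10% certain for a local site under one central list with equal accrual over 5 to 8 sites.

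Varied blocks should not be read as the cure. They cut certainty sharply but guess accuracy by only about 4 percentage points (75% to 71%), and they do nothing about the emailed arm. The order of recording and release is the main issue. Label: cheap improvement.

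**What to change.** **Main.** State in section 6.3 that the week-4 PCDAI, with its components, and the A/B/C assignment are entered and locked in Castor before randomization can run, and that Castor releases the allocation only then. The envelope is then unnecessary; if it is kept, state who prepares it. State also whether the list is central or per site.

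**Secondary.** Use randomly varying blocks of 2 and 4, and hold the sizes in a restricted document outside the protocol. Relax the sentence on equal numbers in A1 and A2 to approximately equal.

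**Cost.** Castor is already both eCRF and randomization tool (section 10.4, version 1.9), so this needs a setting, an entry lock and a few sentences. Section 10.1.7 still names RedCap for the CRF and should be aligned. Randomization would wait for the local blood results that the PCDAI needs, within the ±5-day window. Final A1 and A2 numbers may differ by up to 2 children (mean about 0.2–0.25 for an assumed 6–10 in Group A). No eligibility criterion, treatment or clinical rule changes.

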6.4 STUDY INTERVENTION COMPLIANCE

Subjects in the antibiotic treatment arm will be asked to complete a medication calendar to record the dose and any problems encountered while administering the dose (e.g. vomiting). Study staff will monitor adherence by counting tablets returned at the 12 week visit.

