Subjects will be stratified based on microbiome profile before they are randomized. A baseline stool sample provided at or within 30 days of week 0 will be processed for DNA sequencing and analyzed by a blinded bioinformatician at Dalhousie University. At week 4, subjects will be assigned to Group A or B based on posterior probability of having a 'relapse-associated' microbiome according to an established statistical model. If patients have not achieved clinical remission, they will be assigned to group C to receive antibiotic for 8 weeks. Subjects in Group A will be randomly assigned to continue SOC therapy alone (Group A1) or to receive add-on antibiotic therapy in addition to SOC (Group A2) for the next 8 weeks (week 4-12). Subjects in Group B will continue on SOC therapy alone for the next 8 weeks.

At week 0, a medication calendar will be distributed to all subjects and patients/families will receive teaching on how to complete it for SOC therapy. At week 4, subjects randomized to Group A2 will be given additional instructions on how to complete the calendar for antibiotic treatment. The calendar will be returned to study staff at week 12 to be used as a measure of compliance and adherence.

Pediatric patients with mild to moderate CD are normally started on an immunomodulator during induction therapy to help maintain remission. Although methotrexate is not FDA approved for this purpose, in this study, subjects will receive 15mg/m² subcutaneous (s.c.) methotrexate (MTX) as maintenance therapy (max. 25mg weekly), consistent with several current international guidelines as standard of care⁴⁶, unless there are contraindications, or oral MTX is preferred and/or the patient/family refuses immunomodulatory therapy.⁴⁷ However, the use of MTX is not a condition to take part in this study. The use of MTX is only prescribed under guidance of the treating physician.

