8.3.4 TIME PERIOD AND FREQUENCY FOR EVENT ASSESSMENT AND FOLLOW-UP

The occurrence of an adverse event (AE) or serious adverse event (SAE) may come to the attention of study personnel during study visits of a study participant presenting for medical care, or upon review by a study monitor.

All AEs including local and systemic reactions not meeting the criteria for SAEs will be captured on the appropriate case report form (CRF). Information to be collected includes event description, time of onset, clinician's assessment of severity, relationship to study product (assessed only by those with the training and authority to make a diagnosis), and time of resolution/stabilization of the event. All AEs occurring while on study must be documented appropriately regardless of relationship. All AEs will be followed to adequate resolution.

Any medical condition that is present at the time that the participant is screened will be considered as baseline and not reported as an AE. However, if the study participant's condition deteriorates at any time during the study, it will be recorded as an AE.

Changes in the severity of an AE will be documented to allow an assessment of the duration of the event at each level of severity to be performed. AEs characterized as intermittent require documentation of onset and duration of each episode.

The study clinician will record all reportable events with start dates occurring any time after informed consent is obtained until 7 (for non-serious AEs) or 30 days (for SAEs) after the last day of study participation. At each study visit, the investigator will inquire about the occurrence of AE/SAEs since the last visit. Events will be followed for outcome information until resolution or stabilization.]

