9.4 STATISTICAL ANALYSES

9.4.1 GENERAL APPROACH

All summary tables will be presented by treatment group (Group A1, A2, and B) and, where applicable, by study visits. For descriptive statistics, continuous variables will be summarized with the mean, median, standard deviation, minimum and maximum. Categorical variables will be presented as counts and proportions expressed as a percentage. In addition, summary figures will be generated for longitudinal data to display change in mean or proportion over time.

Missing values in continuous variables will not be imputed. Missing values in categorical variables will be imputed as non-responders.

All tests will be two-sided and considered significant at $P<0.05$. Hypothesis tests that are not statistically significant will be deemed inconclusive. No adjustments to the test-wise error rate will be made.

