10.1.6 SAFETY OVERSIGHT

Safety oversight will be under the direction of a Data and Safety Monitoring Board (DSMB) composed of individuals with the appropriate expertise, including experts in clinical care and trials in pediatric gastroenterology and inflammatory bowel disease. Members of the DSMB should be independent from the study conduct and free of conflict of interest, or measures should be in place to minimize perceived conflict of interest. The DSMB will meet at least semiannually to assess safety and efficacy data on each arm of the study. The DSMB will operate under the rules of an approved charter that will be written and reviewed at the organizational meeting of the DSMB. At this time, each data element that the DSMB needs to assess will be clearly defined. The DSMB will provide its input to the study sponsor [name] [name] as well to [name].

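### In weeks 4–12, tolerability symptoms have more routes to be captured in antibiotic-treated children than in A1 or B, so adverse-event counts by arm and by period may be biased

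*Combined protocol and SAP*

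**What the plan says.** Routes open to every group. The Schedule of Activities (1.3) places adverse-event review at weeks 4, 12, 24, 36 and 52. Section 8.3.4 says that at each visit "the investigator will inquire about the occurrence of AE/SAEs since the last visit". For weeks 4–12 this means one scheduled question, at week 12, in every arm. Section 8.3.4 also picks up events when a participant presents for medical care, and 8.3.5 records spontaneous reports from any subject.

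Routes described only for antibiotic treatment. Section 6.4 asks children in the antibiotic arm to use a calendar to "record the dose and any problems encountered while administering the dose (e.g. vomiting"). Section 6.1.2, on antibiotic dosing, says that patients who suspect intolerance "are advised to contact the study coordinator regarding any new symptoms", and lists emesis, significant nausea, abdominal pain and diarrhoea. Footnote e of the Schedule of Activities gives A2 and C an ECG 2–4 weeks after the drug is started; Section 8.2 names only A2 for the follow-up ECG.

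The controls' calendar. Section 4.1 says that at week 0 "a medication calendar will be distributed to all subjects and patients/families will receive teaching on how to complete it for SOC therapy", and that at week 4 "subjects randomized to Group A2 will be given additional instructions on how to complete the calendar for antibiotic treatment". It describes the calendar, returned at week 12, as a compliance measure. It mentions no symptom entry for controls.

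Where the counts are read. Section 10.1.6: "The DSMB will meet at least semiannually to assess safety and efficacy data on each arm of the study". Section 9.4.1: "All summary tables will be presented by treatment group (Group A1, A2, and B) and, where applicable, by study visits". Section 6.3 confirms that the trial is not blinded. Section 9.4.4 plans no formal safety outcome, and Section 9.3 defines the safety set by at least one week of study intervention.

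**The concern.** Prompted reporting usually finds more than unprompted reporting. If one arm is prompted and the other is not, a difference in recorded events mixes drug effect with detection. Abdominal pain and diarrhoea also occur in Crohn's disease itself, so children in A1 and B will have some of these symptoms without the same prompts to report them.

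The same applies over time within A2. The calendar is returned at week 12 and the drug stops then, so a later fall in A2 events could reflect the end of treatment, the end of extra capture, or both.

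Two features of the plan add to what is at stake. Section 8.3.3.2 lets a temporal relationship support a classification of related, and an entry tied to a dose meets that easily. The Netherlands addendum (Section 12) allows pilot data to be carried into the full-scale trial if the protocol does not change substantially, and unequal capture cannot be corrected after the event.

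**Working it through.** The plan states no adverse-event rate, so there is no figure of its own to reproduce. The check compares capture routes, counts the prompts, and then illustrates the possible size.

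**1. Routes in weeks 4–12**

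| Route | A2 | A1 and B | Section |
|---|---|---|---|
| Inquiry at the week-12 visit | yes | yes | 1.3, 8.3.4 |
| Spontaneous report | yes | yes | 8.3.5 |
| Presentation for care | yes | yes | 8.3.4 |
| Calendar note of problems when taking a dose | yes | not described | 6.4, 4.1 |
| Advice to contact the coordinator on suspected intolerance | yes | does not arise | 6.1.2 |
| ECG 2–4 weeks after starting | yes | no | 1.3, 8.2 |

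After week 12 only the first three rows remain, for everyone. Whether the antibiotic arm in 6.4 includes Group C is not stated; the week-4 calendar instruction in 4.1 names only A2.

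**2. Number of prompts (schedule from 6.1.2, full dosing)**

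- Azithromycin: 5 × 4 + 3 × 4 = 32 doses.
- Metronidazole: 2 × 7 × 8 = 112 doses.
- Total: 32 + 112 = 144 scheduled doses with a request to note problems, against none described for controls.
- Share of follow-up with extra capture: 8 / 52 = 15.4%.

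These are occasions for an entry, not expected events.

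**3. Illustration of size (all rates assumed)**

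Observed proportion = true proportion × capture probability. With the same true proportion p in both arms, the spurious difference is p × (c_A2 − c_A1) and the spurious risk ratio is c_A2 / c_A1. Take p = 30%:

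| Capture, A2 vs A1 | Observed | Difference | Risk ratio | Children at 10 per arm | Children at 5 per arm |
|---|---|---|---|---|---|
| 0.90 vs 0.90 | 27% vs 27% | 0 | 1.00 | 0 | 0 |
| 0.90 vs 0.70 | 27% vs 21% | 6 points | 1.29 | 0.6 | 0.3 |
| 0.90 vs 0.50 | 27% vs 15% | 12 points | 1.80 | 1.2 | 0.6 |

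Ten per arm is the ceiling: 20 children are enrolled (4.1, 9.2) and all would have to enter Group A. Five per arm is an assumption that leaves room for Groups B and C.

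Wider range: with 0.90 against 0.50, p of 20–60% gives 8–24 points, or 0.4–1.2 children at 5 per arm and 0.8–2.4 at 10. An extreme pair, 0.95 against 0.30 at p = 40%, gives 38% against 12%: 26 points, or 1.3 children at 5 per arm and 2.6 at 10.

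**The case against.** The strongest case against is that the calendar is an adherence tool. It sits under the compliance heading, covers problems arising while a dose is taken, and no sentence sends its entries to the adverse-event form. The contact advice is conditional on suspected intolerance to the study drugs and leads into dose management, so it has no direct counterpart in children who do not take them. No safety comparison is planned, and the safety set seems to leave out children on standard of care alone if study intervention means the antibiotics. The DSMB's data elements are left to a charter that is not part of the documents. With arms this small, a difference of 6–12 points could not be interpreted anyway.

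Most of this stands, and it limits the point to descriptive and DSMB summaries. It does not remove the asymmetry. Section 8.3.4 requires all adverse events on study to be documented whatever their cause, so vomiting noted on a returned calendar or reported to the coordinator would ordinarily become a record. If that is not intended, the plan should say so.

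Stronger readings are tempting, but the documents do not support them:

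- A reader might infer that controls are questioned only once while A2 is questioned repeatedly. The week-12 inquiry is the same in every arm, and controls also have spontaneous reporting and presentation for care.
- A reader might infer a programme of telephone calls to treated children. Section 6.1.2 says only that they should make contact, and gives no mode.
- A reader might infer that event rates must differ whatever the drug does. Only the opportunity for capture differs; if recall at week 12 captured as much, no difference would appear.

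**Conclusion.** The point holds as a potential detection bias. In weeks 4–12 antibiotic-treated children have more described routes by which tolerability symptoms can come to notice than A1 or B, and the plan makes no allowance for this where safety is read by arm or by visit. Counts by arm and by period may be biased, most plausibly towards more recorded events in A2 during treatment.

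The size cannot be found from the documents. Under the assumed 30% true proportion and 90% against 50–70% capture, the artefact is about one child or fewer per arm; it exceeds one child clearly only under more extreme assumptions or larger arms. No formal safety test is affected. The judgement assumes that calendar and contact reports reach the adverse-event form, which is not stated, and that the controls' calendar has no symptom field, since none is described. This is a cheap improvement to make before the design is scaled up, not a threat to the pilot's validity.

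**What to change.** For weeks 4–12:

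- Put the same short symptom line on the calendar for A1, A2, B and C. All groups already hold the calendar.
- Give every group the same advice to report new symptoms to the coordinator.
- Record the source of each event on the adverse-event form (visit inquiry, calendar, contact, ECG visit), and state that calendar entries are reviewed for it.
- Keep all events in the DSMB reports. Show by-arm counts overall and by source, so that unequal capture is visible.

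The source field alone would not be enough, because a calendar handed in at week 12 can prompt answers to that visit's inquiry. The common symptom line does most of the work. The ECG contact stays unequal, and the source field makes that visible. The cost is one calendar line, one form field, a sentence of instruction and slightly more diary burden for controls.
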